8. STATISTICAL METHODOLOGY AND STATISTICAL ANALYSES

A modified treatment-policy estimands strategy is applied as the main strategy to assess effectiveness of tanezumab. Data collected will be included for efficacy assessment regardless of rescue medication being used or not.

The general study design for efficacy includes a planned treatment period through the Week 56 visit, and a planned 24-week post-treatment safety follow-up period. Efficacy data planned to be collected during this post-treatment safety follow-up period are intended to have efficacy measures contemporaneous to safety observations during this period. They are not intended to assess treatment effects or compare treatment groups. *All endpoints up to Week 64 will be summarized (where available), and endpoints up to Week 56 will be analyzed.*

The method and definition of reporting windows for assigning efficacy data to particular time points is described in [Appendix 1.1](#).

All efficacy assessments are made on the analysis windows defined in [Appendix 1](#). Using these windows we find the analysis window for a patient’s last subcutaneous (SC) dose. Any data included in a window up to 8 weeks from this last SC dose window is ‘on-treatment’, and any in a window more than 8 weeks after the last SC dose window is off treatment. Data in on-treatment analysis windows will be used in summaries and analyses, while data in off-treatment analysis windows will be excluded from all summaries and analyses of treatment period efficacy data, ie, up to Week 56.

For example the table below shows on-treatment and off-treatment windows for the planned collection visits for the WOMAC data during the treatment period:

Last SC Dose Analysis Window	On-treatment Analysis Window Data	Off-treatment Analysis Window Data
Baseline	Weeks 2, 4, 8	Weeks 16, 24, 32, 40, 48, 56
Week 2	Weeks 2, 4, 8	Weeks 16, 24, 32, 40, 48, 56
Week 4	Weeks 2, 4, 8,	Weeks 16, 24, 32, 40, 48, 56
Week 8	Weeks 2, 4, 8, 16	Weeks 24, 32, 40, 48, 56
Week 16	Weeks 2, 4, 8, 16, 24	Weeks 32, 40, 48, 56
Week 24	Weeks 2, 4, 8, 16, 24, 32	Weeks 40, 48, 56
Week 32	Weeks 2, 4, 8, 16, 24, 32, 40	Weeks 48, 56
Week 40	Weeks 2, 4, 8, 16, 24, 32, 40, 48	Week 56
Week 48	Weeks 2, 4, 8, 16, 24, 32, 40, 48, 56	None
Week 56	Weeks 2, 4, 8, 16, 24, 32, 40, 48, 56	None

0900177e4193181b656Approved\Approved On: 08-10-2019 08:56 (GMT)

Efficacy data at Week 64 is planned to be off-treatment so will not be subject to the above handling, ie, all available data in the Week 64 window will be used in summaries.

Efficacy data collected via subject diary (NRS pain scores and rescue medication use) are collected daily or weekly, not at study visits. Diary efficacy data will be considered on-treatment if it is collected up to 12 weeks (84 days) after the last SC dose. Diary efficacy data collected more than 12 weeks (84 days) after the last SC dose will be considered off-treatment and excluded from summaries and analyses of treatment period efficacy data, ie, for presentations up to Week 56.

Diary data after Week 56 is planned to be off-treatment so will not be subject to the above handling, ie, all available data in windows after Week 56 will be used in summaries.

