# 6.4.1.1. Early Termination Follow-up Visit 1 (8 weeks after last dose of SC investigational product treatment)

- Adverse events review.
- WOMAC (all subscales).
- Patient's Global Assessment of Osteoarthritis.
- WPAI:OA.
- EQ-5D-5L.
- TSQM (v.II).
- mPRTI.
- Lower Extremity Activity Scale (LEAS).
- Survey of Autonomic Symptoms (SAS).
- Vital signs after sitting for at least 5 minutes, (blood pressure, and heart rate).
- Orthostatic blood pressure (supine/standing) measurement.
- ECG (12-lead).
- Body weight.
- General physical examination.
- Musculoskeletal physical examination.

- Neurologic exam/Neuropathy Impairment Score (referral for neurological consult if required).
- Review/update of concomitant medication.
- Assess compliance with weekly IRT entries (weekly index joint pain score, weekly non-index joint pain assessment and as applicable, weekly rescue medication and weekly NSAID use entries).
- Monitor for violations of concomitant NSAID use.
- Review weekly joint pain scores.
- Rescue medication (acetaminophen / paracetamol) compliance review/dispense.
- Serum pregnancy test for females of childbearing potential.
- Serum and plasma retention samples.
- Blood sample for anti-tanezumab antibody assessment (refer to Section 7.3.14).
- Blood samples for PK and PD (NGF) analyses (refer to Section 7.5).
- For subjects that performed activity level monitoring via accelerometry, blood and urine samples for biomarkers (fasting if possible, urine sample should be from 2nd void of the day or after; refer to Section 7.6).
- Reminder to females of child-bearing potential to continue with contraceptive requirements.
- If arthrocentesis will be performed for a subject (refer to Section 7.4.7) and the subject has provided the applicable informed consent, collect a synovial fluid sample (refer to Section 7.5.3).

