6.1. Efficacy Endpoint(s)

The co-primary efficacy endpoints are listed below.

- *Change from Baseline to Week 16 in the Western Ontario and McMaster Universities Osteoarthritis Index (WOMAC) Pain subscale.*
- *Change from Baseline to Week 16 in the WOMAC Physical Function subscale.*
- *Change from Baseline to Week 16 in the Patient's Global Assessment of Osteoarthritis (Note, this is not a primary endpoint for Japan).*

The secondary efficacy endpoints are listed below.

- *WOMAC Pain subscale change from Baseline to Weeks 2, 4, 8, 24, 32, 40, 48, 56 and Week 64.*
- *WOMAC Physical Function subscale change from Baseline to Weeks 2, 4, 8, 24, 32, 40, 48, 56 and Week 64.*
- *Patient's Global Assessment of Osteoarthritis change from Baseline to Weeks 2, 4, 8, 16 (Japan only), 24, 32, 40, 48, 56 and Week 64.*
- *OMERACT-OARSI responder index at Weeks 2, 4, 8, 16, 24, 32, 40, 48, 56 and Week 64.*
- *Treatment Response: Reduction in the WOMAC Pain subscale of $\geq 30\%$, $\geq 50\%$, $\geq 70\%$ and $\geq 90\%$ at Weeks 2, 4, 8, 16, 24, 32, 40, 48, 56 and Week 64.*
- *Cumulative distribution of percent change from Baseline in the WOMAC Pain subscale score to Week 16, 24, and 56 (endpoint for summary only).*
- *Treatment Response: Reduction in the WOMAC Physical Function subscale of $\geq 30\%$, $\geq 50\%$, $\geq 70\%$ and $\geq 90\%$ at Weeks 2, 4, 8, 16, 24, 32, 40, 48, 56 and Week 64.*
- *Cumulative distribution of percent change from Baseline in the WOMAC Physical Function subscale score to Week 16, 24, and 56 (endpoint for summary only).*
- *Treatment Response: Improvement of ≥ 2 points in Patient's Global Assessment of Osteoarthritis at Weeks 2, 4, 8, 16, 24, 32, 40, 48, 56 and Week 64.*
- *Average pain score in the index joint change from Baseline to Weeks 1, 2, 3, 4, 6, 8, 10, 12, 16, 20, 24, 32, 40, 48, 56 and Week 64.*
- *WOMAC Stiffness subscale change from Baseline to Weeks 2, 4, 8, 16, 24, 32, 40, 48, 56 and Week 64.*

09001776e193181b6561Approved\Approved On: 08-10-2019 08:56 (GMT)

- *WOMAC Average change from Baseline to Weeks 2, 4, 8, 16, 24, 32, 40, 48, 56 and Week 64.*
- *WOMAC Pain Subscale Item: Pain When Walking on a Flat Surface, change from Baseline to Weeks 2, 4, 8, 16, 24, 32, 40, 48, 56 and Week 64.*
- *WOMAC Pain Subscale Item: Pain When Going Up or Down Stairs, change from Baseline to Weeks 2, 4, 8, 16, 24, 32, 40, 48, 56 and Week 64.*

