Visit	Target Study Day	Window
Baseline	1 (defined as initial day of study drug administration)	[-7, 1]
Week 8	57	[2, 85]
Week 16	113	[86, 141]
Week 24	169	[142, 225]
Week 40	281	[226, 337]
Week 56	393	[338, 421]
Week 64	449	[422, no upper limit]

WPAI: OA

Visit	Target Study Day	Window
Baseline	1 (defined as initial day of study drug administration)	[-7,1]
Week 16	113	[2,141]
Week 24	169	[142,281]
Week 56	393	[282, 421]
Week 64	449	[422, no upper limit]

Actigraphy, TSQM, mPRTI

Visit	Target Study Day	Window
Baseline	1 (defined as initial day of study drug administration)	[no lower limit, 1]
Week 16	113	[2,253]
Week 56	393	[254, no upper limit]

0900177ed193781b656Approved\Approved On: 08-10-2019 08:56 (GMT)

HCRU

Visit	Target Study Day	Window
Baseline	1 (defined as initial day of study drug administration)	[no lower limit, 1]
Week 64	449	[2,505]
Week 80	561	[506, no upper limit]

For the average pain in the index joint, the data are collected daily via electronic diary up to the end of Week 16, and thereafter weekly up to Week 80. Data up to Week 64 will be reported as part of the efficacy assessment (summary up to Week 64; analysis up to Week 56).

The Baseline score is the mean of the last 3 non-missing pain scores over study days -7 to -1. If fewer than 3 are available between study days -7 and -1, the baseline will be the mean of the available scores.

The table below describes the visit days for each week (Weeks 1-16). All available on-treatment diary data in each of the weekly intervals will be used to calculate the mean daily pain score for that study week.

09001776e1931781b656\Approved\Approved On: 03-10-2019 08:56 (GMT)

Study Week	Days	Study Week	Days
1	1-7	9	57-63
2	8-14	10	64-70
3	15-21	11	71-77
4	22-28	12	78-84
5	29-35	13	85-91
6	36-42	14	92-98
7	43-49	15	99-105
8	50-56	16	106-112

However, if a subject receives the Week 16 injection dose prior to Day 113, the Week 16 score will be calculated using the mean of the available scores from the 7 calendar days immediately prior to the Week 16 injection dose date. Any scores used in this calculation of Week 16 will not also be used in an earlier week calculation, eg, if the Week 16 dose occurs on Day 109, the available scores from Days 102-108 will be used to calculate the average score for Week 16, and the available scores from Days 99-101 will be used to calculate the average score for Week 15.

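### The on-treatment rule compares window labels, so some TSQM, mPRTI and WPAI:OA scores taken 8 weeks after the last injection are discarded as off-treatment

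*SAP*

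**What the plan says.** **The rule.** SAP section 8 places the last SC dose in an analysis window and compares windows. The category that counts as on treatment is "Any data included in a window up to 8 weeks from this last SC dose window". Scores in later windows fall on the other side of the line and lose their place in the treatment-period results: "data in off-treatment analysis windows will be excluded from all summaries and analyses of treatment period efficacy data", with Week 56 as the end of that period. The worked table is only an illustration for one instrument: "For example the table below shows on-treatment and off-treatment windows for the planned collection visits for the WOMAC data during the treatment period".

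**Its reach.** In SAP section 6.1, the list that opens "The secondary efficacy endpoints are listed below" includes TSQM, mPRTI, WPAI:OA and EQ-5D-5L. Section 8 makes no exception for instruments with broad windows.

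**The windows.** In SAP Appendix 1.1 the table headed "Actigraphy, TSQM, mPRTI" has two post-baseline windows, Week 16 (Days 2 to 253) and Week 56 (Day 254 onward). WPAI:OA and EQ-5D-5L also have broader windows than WOMAC.

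**When the score is taken.** Protocol 6.4.1.1 is headed "Early Termination Follow-up Visit 1 (8 weeks after last dose of SC investigational product treatment". All four instruments are collected at that visit, and in the early termination schedule it is the only visit with TSQM and mPRTI.

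**Elapsed-time limits elsewhere.** For diary data SAP section 8 counts days: "Diary efficacy data will be considered on-treatment if it is collected up to 12 weeks (84 days) after the last SC dose". Protocol 9.2.2 allows Week 64 visit data from early discontinuers if taken within 10 weeks of the last dose.

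**Missing data.** SAP 8.2.2 (items 9 and 10) and the table in SAP 8.2.5 analyse TSQM, mPRTI and WPAI:OA on observed data without imputation. EQ-5D-5L is summarised only.

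**The concern.** Take a subject who receives only the Day 1 injection and attends Early Termination Visit 1 on Day 57. The WOMAC score from that visit falls in the Week 8 window (Days 44 to 85), so it is on-treatment and kept. The TSQM and mPRTI scores from the same visit fall in the Week 16 window. Week 16 is off-treatment after a Baseline last dose, so they are dropped. Subject, visit and elapsed time are the same; only the window width differs.

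The excluded subjects are defined by when they stopped treatment, which happens after randomisation and can differ between arms. TSQM is tested by ANCOVA and mPRTI by a CMH test on observed data, so a dropped score removes the subject from that comparison. A window that opens on Day 2 appears meant to catch early scores, and the label rule then discards the earliest of them.

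**Working it through.** **Step 1: confirm how the rule operates.** Call a score on-treatment if

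label of score window − label of last-dose window ≤ 8 weeks.

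Applied to the WOMAC windows, this reproduces all 10 rows of the SAP's table. The alternative is to use the gap between window edges (start of score window − end of dose window ≤ 56 days). It reproduces 9 of 10: for a Week 4 last dose, 86 − 43 = 43 days would make Week 16 on-treatment, and the table says off. The SAP therefore compares labels.

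**Step 2: inputs.**
- Planned dose days: 1, 57, 113, 169, 225, 281, 337. Early-termination score day = dose day + 56.
- Dose label: from the main visit windows in Appendix 1.1.
- TSQM/mPRTI: Week 16 = 2–253, Week 56 = 254 onward.
- WPAI:OA: Week 16 = 2–141, Week 24 = 142–281, Week 56 = 282–421.
- EQ-5D-5L: Week 8 = 2–85, Week 16 = 86–141, Week 24 = 142–225, Week 40 = 226–337, Week 56 = 338–421.

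**Step 3: results on target days.** Each cell gives the score's label, the label difference in weeks, and the status.

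| Last dose | Score day | TSQM/mPRTI | WPAI:OA | EQ-5D-5L |
|---|---|---|---|---|
| Baseline | 57 | 16, 16, **off** | 16, 16, **off** | 8, 8, on |
| Week 8 | 113 | 16, 8, on | 16, 8, on | 16, 8, on |
| Week 16 | 169 | 16, 0, on | 24, 8, on | 24, 8, on |
| Week 24 | 225 | 16, −8, on | 24, 0, on | 24, 0, on |
| Week 32 | 281 | 56, 24, **off** | 24, −8, on | 40, 8, on |
| Week 40 | 337 | 56, 16, **off** | 56, 16, **off** | 40, 0, on |
| Week 48 | 393 | 56, 8, on | 56, 8, on | 56, 8, on |
| Dropped | | 3 of 7 | 2 of 7 | 0 of 7 |

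WOMAC drops 0 of 7.

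**Step 4: visit tolerance of ±7 days.** The TSQM/mPRTI losses after Week 32 and Week 40 hold for every dose day in the tolerance. EQ-5D-5L loses a 56-day score only if the Week 24 dose falls on Days 170–176 (score Days 226–232, labelled Week 40, difference 16) or the Week 40 dose on Days 282–288 (score Days 338–344, labelled Week 56, difference 16). A visit 1 to 7 days late after an on-time dose has the same effect. WPAI:OA also loses the Week 32 case if the dose or the visit is late. Over 1 + 6 × 15 = 91 possible dose days, the drops are WOMAC 0, EQ-5D-5L 14, WPAI:OA 23 and TSQM/mPRTI 31. These count calendar days, not subjects.

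**Step 5: the conflict between rule and window.** A Week 56 label is on-treatment only if the last-dose label is at least 56 − 8 = 48, and the main Week 48 window opens on Day 310. So Days 254–309 of the TSQM/mPRTI Week 56 window cannot supply an on-treatment score taken after the last dose. Likewise a Week 16 label needs a last-dose label of at least 8, and that window opens on Day 44, so Days 2–43 cannot supply one either.

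**Step 6: an elapsed-day rule.** 56 ≤ 70 (10 weeks) and 56 ≤ 84, so either existing limit keeps the score in all 7 rows for every instrument.

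**The case against.** *A Day 57 score after one injection is not a Week 16 result, so excluding it is reasonable.* This stands as a view on the estimand. But the window table decides which time point a score represents, and it assigns Day 57 to Week 16. It also assigns Day 225, after four injections, to Week 16 and calls it on-treatment. If the sponsor does not want such scores at Week 16, narrowing the window would say so openly. An elapsed-day rule does not settle this question, so it needs its own statement.

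*The main non-response stop is not affected.* Correct. Subjects stopped at Week 16 for insufficient pain reduction complete TSQM and mPRTI at that visit, normally after a Week 8 dose, and those scores are kept.

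*A reader might infer that about half of on-schedule completers lose their Week 56 EQ-5D-5L score.* That follows only if the injection is placed in EQ-5D-5L's own windows. A Week 48 dose on Days 330–337 of 330–344 (8 of 15 days) would then be labelled Week 40. The documents do not support this reading. The SAP's table has last-dose rows for Weeks 32 and 48, which exist in the main visit windows and not in the EQ-5D-5L ones, and Appendix 1.1 keeps the broader windows for assessments not made at every planned visit. With the main windows a Week 48 dose on Days 330–344 is labelled Week 48 and the Day 393 score is kept. What stands is that the SAP does not say outright which windows place the dose. The own-window reading would give TSQM/mPRTI losses at Baseline and Week 32 only. Those two losses occur under either reading.

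**Conclusion.** The concern holds in a limited form. The label rule, applied as the SAP's own table applies it, marks some scores taken 56 days after an injection as off-treatment:

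- TSQM and mPRTI after last doses at Baseline, Week 32 and Week 40;
- WPAI:OA after last doses at Baseline and Week 40;
- EQ-5D-5L only when the Week 24 or Week 40 dose, or the visit after it, is late.

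It would be wrong to infer that every 8-week score is lost: TSQM and mPRTI keep 4 of the 7 cases. After last doses at Weeks 16 and 24 the early-termination score, though on-treatment, would usually give way to the Day 113 score, which is nearer the Week 16 target. It would also be wrong to put a figure on subjects lost or on the shift in a treatment difference. The documents give no counts of early stops by last dose and no scores for those subjects.

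The co-primary WOMAC and PGA analyses are untouched, and the affected endpoints are secondary and outside multiplicity control. The result assumes that the main visit windows place the dose and that early-termination visits occur near their target. The change is still worth making: the exclusion depends on when treatment stopped, and it follows from window width rather than from a stated decision.

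**What to change.** 1. For TSQM, mPRTI, WPAI:OA, EQ-5D-5L and other broad-window visit assessments, define on-treatment by actual days since the last SC dose. Apply this first, then assign the retained score to its Appendix 1.1 window. The order matters for WPAI:OA: a single-injection subject also has a score at Early Termination Visit 2 (Day 1 + 112 = Day 113), which would displace the Day 57 score if the score nearest the target day were chosen first.
2. Use one limit, reconciling the protocol's 10 weeks with the SAP's 84-day diary limit. Do not justify 84 days as the widest span of the visit windows: a dose on Day 86 and a score on Day 197 are 111 days apart, yet lie in the adjacent Week 16 and Week 24 windows.
3. Where the label rule stays, as for WOMAC and PGA, state that the main visit windows place the last dose.
4. Report how many early-termination scores contribute to each Week 16 and Week 56 result.

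The cost is a few sentences in SAP section 8, a date comparison in programming and one count per table. No new data are needed.

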8.1. Statistical Methods

8.1.1. Analyses for Continuous Data

The mixed model ANCOVA, with multiple imputation, will be used with continuous change from Baseline endpoints for landmark (single time point) analyses. The model will include the covariates described in [Section 6.4](#), including study site as a random effect. Estimates of treatment effects and pair wise treatment comparisons will be done using least squares means (LS means) and 95% CIs.

Under the primary analysis using multiple imputation defined in [Section 7](#), the multiple ANCOVA results will be combined using standard methods (Little & Rubin, 2002)³, which are described in [Appendix 3.2](#).

A sensitivity analysis for the primary endpoints will use a mixed model repeated measures analysis, with covariate terms for Time (study week, treated as a categorical variable), Treatment Group and Time-by-Treatment interaction, as well as the covariates described in [Section 6.4](#). The unstructured covariance will be used in the modeling of the within-subject errors in the analysis. Even though this is a sensitivity analysis for the primary endpoints, estimates for the time points of Weeks 2, 4, and 8, in addition to Week 16 will be shown from this analysis.

Interaction analyses will be performed for the primary endpoints, exploring the effect of Study site and Country. These analyses will fit the covariate terms described in [Section 6.4](#) (except for use of Study site as a covariate in the Country interaction analysis, where Country will be used instead [as a fixed term]), in addition to the interaction term of treatment group by factor.

The interaction of Treatment with Study site will be fitted as a random effect (in addition to Study site itself), with the resulting estimated treatment differences being shown for the largest study sites to illustrate the level of consistency of treatment benefit across the larger study sites. The study sites to be examined in this way will be any site with an average of ten or more subjects per treatment group within the site, which for this study relates to any site with 30 or more subjects in total. This assessment will be made prior to unblinding, therefore a study site in this group may still have fewer than ten subjects in one or more of the treatment groups, however that site will still be included in this summary of efficacy of the

0900177ed193181b050ApprovedApproved On: 03-Oct-2019 08:56 (GMT)

largest study sites. To aid the interpretation of the treatment-site and treatment-country interactions, a summary of the efficacy data for each co-primary endpoint by treatment group will be shown for the sites with ≥ 30 subjects and also for the countries with ≥ 30 subjects over all treatment groups.

The time to discontinuation from treatment due to lack of efficacy will be analyzed using the log-rank test, and estimated failure curves will be produced using Kaplan-Meier estimation. The time to selected percentiles will also be shown. These are influenced by the frequency of discontinuation, but are expected to be shown for the 1st, 2nd, 5th, 10th and 25th percentiles, in addition to the minimum and maximum time to discontinuation. Any subject who discontinues for any other reason prior to the planned Week 56 visit will be censored at the time of discontinuation. Subjects who complete the study or who discontinue for any reason after the Week 56 visit (including lack of efficacy) will be censored at the Week 56 visit. This analysis will be performed using 'Insufficient clinical response' alone, and either 'Insufficient clinical response' or 'Patient meets protocol specified pain criteria for discontinuation', as reasons for discontinuation.

The time to joint safety events will be summarized and analyzed in the same way as described above for the time to discontinuation due to lack of efficacy. For these analyses, subjects without events would be censored up to the end of the observation period (defined as end of study completion or discontinuation for subjects who did not have an event). Time to the earliest event would be considered for those who had multiple events.

8.1.2. Analyses for Categorical Data

The number of days and amount (mg of acetaminophen/paracetamol) of rescue medication used per week will be analyzed using a negative binomial model with model terms of treatment group and covariates as described in [Section 6.4](#). In this model the error term is defined with a negative binomial distribution, and 'log' is used as the link function. Output from this analysis will be the estimated number/amount of rescue medication use per week in each treatment group, and (following the exponential back transformation) the ratio of rescue medication use for the treatment comparisons shown in [Section 4.1](#). The 95% CIs will be given for the estimates of both the individual treatment groups and the treatment group ratios.

The change from Baseline in the NIS will be analyzed using a Cochran-Mantel-Haenszel (CMH) test for 'row mean scores differ', using change from Baseline categories as the scores in the analysis, and stratified by the combined levels of the three stratification factors ([Section 6.4](#)). Output will show number and percentage of subjects whose NIS score worsened (change >0), improved (change <0) or had no change, in addition to the mean (with standard deviation) and median change, and minimum and maximum change. This analysis will be performed for the two treatment comparisons separately, and shown by visit and worst change (largest change from baseline to any post-baseline visit), and by last change (summary statistics only).

090017764931781b656\Approved\Approved On: 03-Oct-2019 08:56 (GMT)

The change from Baseline in the Patient's Global Assessment of Osteoarthritis to Weeks 2, 4, 8, 16, 24, 32, 40, 48, and 56 will also be analyzed using the CMH test and stratified by the combined levels of the stratification factors. Changes by each level of improvement will be summarized, as well as any improvement (change<0), and any worsening (change>0). For this analysis imputation for missing data will use mixed BOCF/LOCF, BOCF, and LOCF.

The change from Baseline in the Lower Extremity Activity Scale to Weeks 4, 8, 16, 24, 56 and 80 and worst post-Baseline score will be analyzed using CMH test and stratified by the combined levels of the three stratification factors (Section 6.4). LOCF will be used for imputation of missing data. The change from Baseline to all weeks (including Week 80) will be summarized showing the number and percentage of subjects with any worsening score (change<0), no change, or improvement (change>0), as well as each category of change, and mean (with standard deviation) and median change.

The CMH test will be stratified by the combinations of the three stratification factors (Section 6.4). For any analysis using the CMH test, if there are too few subjects in any stratification combination group (defined as <15 subjects in any stratification factor) then an unstratified test will be performed.

